3.3 Treatment of Subjects and Rationale for Treatment

Panhematin TM 4 mg/kg will be reconstituted with 25% human albumin ⁵⁰ and infused over a 1 hour period. The amount of albumin is based on achieving a 1:1 molecular ratio for hemin and albumin 43,50 . Product labeling suggests that

Panhematin[™], after reconstitution with sterile water, be infused within 15 minutes. After reconstitution with albumin, an infusion time of 1 hour is based on guidelines for infusion of the amount of human albumin used for reconstitution. The longer infusion time of 1 hour is acceptable given the enhanced stability of hemin in the presence of albumin, and based on experience of investigators in the Porphyrias Consortium ⁹.

Glucose infusions will be permitted during the study for treatment of acute attacks. Its use will be recorded but will not be specified by the study. For treatment of acute attacks, Panhematin[™] product labeling suggests an initial trial of glucose at a dose of 400 grams daily, whereas a dose of 300 grams daily as 10% glucose is generally accepted ^{9,68-70} and a higher dose given as 10% glucose may increase the risk of fluid overload and hyponatremia. Smaller amounts (e.g. 200 grams as 2L 5% glucose in saline) have been recommended for meeting fluid, electrolyte and caloric needs, but not as an alternative to hemin therapy ⁷¹. There are no guidelines or published experience for glucose loading for prevention of attacks, but based on expert experience the impression is that it is not very effective and may lead to unwanted weight gain.

Symptomatic treatment, including opioids, needed to control pain and other symptoms during an attack that occurs during the study will be recorded. Use of medications needed to control chronic symptoms, including pain, will also be recorded.

4. Trial Population

4.1 Number of patient and sites

Patients to be randomized: 20

Patients to be evaluated and screened: 40

Approximately 2 patients will need to be evaluated for every patient found suitable for study and randomization. Patients who do not complete the study will need to be replaced.

This study will be conducted at UTMB. Although it will not be a project of the Porphyrias Consortium, which has been funded in part by a U54 grant from the National Institutes of Health (NIH) beginning in 2009, the other sites in the Consortium are aware of this protocol and will refer patients that seem appropriate for evaluation. The Porphyrias Consortium is one of 23 NIH-funded consortia that comprise the Rare Disease Clinical Research Network (RDCRN). Funds for the Porphyrias Consortium U54 grant is provided by the National Institute for Diabetes, Digestive and Kidney Diseases (NIDDK) and the NIH Office of Rare Diseases Research. At present, the Consortium consists of 6 sites funded by the NIH grant, and 2 satellite sites that receive some support from the American Porphyria Foundation.

The American Porphyria Foundation (APF) is an active patient support group and is a supporting partner in the Porphyrias Consortium. The U54 grant supports

Porphyria Laboratory and Center Date: June 18, 2019 IND 13,929

infrastructure for clinical research on porphyrias but not the costs of major clinical trials. Funding by the FDA Office of Orphan Product Development beginning in September 2014 supports costs for this study and an acute treatment study, which is also a Porphyrias Consortium single-site study conducted at UTMB. Recordati Rare Diseases, the manufacturer of Panhematin[™], provides some additional grant support for both studies and supplies study drug at no cost.

4.2 Recruitment of Subjects

The investigators will contact patients known to them who are likely to be eligible for the trial by phone. Many of these patients will already be in contact with the Porphyrias Consortium. Additional patients will be referred by the American Porphyria Foundation (APF), which has been an important referral source for previous porphyria studies. Those patients not previously known to the study team at UTMB, the APF and the Porphyrias Consortium will be contacted through their primary treating physician. Patients newly referred will also be considered and enrolled for screening to determine if they meet the entry criteria. Written material and transcripts of planned verbal descriptions of the study will be approved in advance by the Institutional Review Board (IRB) at UTMB. A Screening Log will be kept of all subjects who are contacted by phone.

4.3 Inclusion Criteria

- 1. Male or female aged \geq 18 years
- 2. Willing to provide written informed consent
- 3. A diagnosis of AIP, HCP or VP confirmed by the following criteria, which are based on the criteria for enrollment in the Longitudinal Study of the Porphyrias Consortium. For each type of porphyria, the inclusion criteria are based on 1) clinical features, 2) biochemical findings, as documented by laboratory reports (or copies) of porphyria-specific testing, and 3) molecular studies to identify a mutation in a porphyria-related gene. Equivocal biochemical measurements may require confirmatory testing. DNA testing is now considered standard of care and will not need to be done as part of this study. DNA testing for acute porphyrias is available through participation in the Porphyrias Consortium's Longitudinal Study (IRB#10-183), and is done by the CAP-approved laboratory at Mt. Sinai, which is the molecular laboratory resource for the Consortium. Such testing is also offered by major referral laboratories such as Mayo and GeneDx, and is currently offered at no cost by inVitae as part of a porphyria testing program supported by Alnylam Pharmaceuticals. An identified mutation is not essential for enrollment, since it is known that a mutation cannot be found in a small fraction (<5%) of biochemically proven cases of porphyria.

Diagnostic inclusion criteria:

Acute intermittent porphyria (AIP):

1. Clinical features – a history of consistent clinical features such as acute attacks of abdominal, back and/or limb pain

- 2. Biochemical findings:
 - a. A marked increase in urinary or serum PBG before treatment with Panhematin[™].
 - i. Urinary PBG >8 mg/24 hours or g of creatinine, or >2 fold increase (relative to upper limit of normal (ULN) of 4 mg/24 hours or mg/g creatinine)
 - ii. Serum PBG >0.2 ug/dL, or >2 fold increase (relative to ULN of 0.1 ug/dL)
 - iii. Marked increases are expected at initial diagnosis and before treatment with Panhematin[™]. But increases may be less marked in patients already on prophylactic treatment with Panhematin[™].
 - b. Normal or only slight increases in plasma and fecal porphyrins.
 - i. Plasma porphyrins <4.5 ug/dL, or <5-fold increase (relative to ULN of 0.9 ug/dL); fluorescence scanning at neutral pH should show no peak or a small peak at ~620 nm. *Note*: AIP patients with severe renal disease are an exception and may have substantial increases in plasma porphyrins.
 - ii. Total fecal porphyrins <400 ug/g dry weight or <2-fold increase (relative to ULN of 200 ug/d dry weight
 - c. Erythrocyte HMBS/PBGD activity deficient in ~90% of cases
 - i. Activity should be below the lower limit of normal, or <60% of the normal mean for the laboratory; this enzyme activity may be falsely low due to improper sample handling or physiologically increased when erythrocyte turnover is increased.
- 3. Molecular findings known:

a. Disease-causing mutation in *HMBS* (also known as *PBGD*) in >95% of cases.

b. Biochemical criteria will suffice if no mutation can be identified.

4. Previous acute attacks of porphyria, consisting of symptoms such as abdominal, back and/or limb pain, diagnosed by the investigator as caused by porphyria after exclusion of other causes, and currently on a prophylactic regimen of Panhematin[™].

Hereditary coproporphyria (HCP):

1. Clinical features – a history of consistent clinical features such as acute attacks of abdominal, back and/or limb pain

- 2. Biochemical findings:
 - a. A marked increase in urinary or serum PBG and/or in urinary coproporphyrin III before treatment with Panhematin™.
 - i. For urinary and serum PBG, same as for AIP (see above)
 - ii. For urinary total porphyrins: >450 nmol/24 hours or g of creatinine, or more than 1.5-fold increase (relative to ULN of 300 nmol/24 hours or g of creatinine
 - b. Normal or only slight increases in plasma porphyrins.
 - Plasma porphyrins <5 ug/dL, or <5-fold increase (relative to ULN of 0.9 ug/dL); fluorescence scanning at neutral pH should show no peak or a small peak at ~620 nm. *Note:* this criterion applies to HCP patients without skin lesions. Skin lesions are rare in this disease, but if present are often accompanied by substantial increases in plasma porphyrins. An exception will be made for this criterion in such cases.
 - c. A substantial increase in fecal porphyrins, with a predominance of coproporphyrin III.
 - i. Total fecal porphyrins >400 ug/g dry weight or >2-fold increase (relative to ULN of 200 ug/g dry weight, with a predominance of coproporphyrin III and a coproporphyrin III/I ratio >1.5
- 3. Molecular findings known:
 - a. Disease-causing mutation in *CPOX* in >95% of cases.
 - b. Biochemical criteria will suffice if no mutation can be identified.
- Previous acute attacks of porphyria, consisting of symptoms such as abdominal, back and/or limb pain, diagnosed by the investigator as caused by porphyria after exclusion of other causes, and currently on a prophylactic regimen of Panhematin[™].

Variegate porphyria (VP):

1. Clinical features – a history of consistent clinical features such as acute attacks of abdominal, back and/or limb pain

- 2. Biochemical findings:
 - a. A marked increase in urinary or serum PBG and/or in urinary coproporphyrin III (same criteria as for HCP) before treatment with Panhematin[™].

- b. Increases in plasma porphyrins and a fluorescence emission peak at ${\sim}626~\text{nm}.$
 - i. Plasma porphyrins >2.7 ug/dL, or >3-fold increase (relative to ULN of 0.9 ug/dL)
 - ii. Fluorescence scanning at neutral pH showing a peak at ~626 nm.
 - c. Substantial increase in fecal porphyrins, with a predominance of coproporphyrin III and protoporphyrin IX.
 - i. Total fecal porphyrins >400 ug/g dry weight or >2-fold increase (relative to ULN of 200 ug/d dry weight, with a predominance of coproporphyrin III and protoporphyrin
- 3. Molecular findings known:
 - a. Disease-causing mutation in *PPOX* in >95% of cases.
 - b. Biochemical criteria will suffice if no mutation can be identified.
- 5. Previous acute attacks of porphyria, consisting of symptoms such as abdominal, back and/or limb pain, diagnosed by the investigator as caused by porphyria after exclusion of other causes, and currently on a prophylactic regimen of Panhematin[™].

4.4 Exclusion Criteria

- 1. Symptoms such as abdominal, back or limb pain are explained by another condition, as judged by the investigator
- 2. Known or suspected allergy to Panhematin[™] or related products
- 3. A known or suspected allergy to human albumin
- 4. Any disease or condition that the investigator judges would lead to an unacceptable risk to the patient or interfere with the successful collection of data for the trial
- 5. Previous randomization in this trial

All inclusion and exclusion criteria must be satisfied for inclusion of a patient in the efficacy analysis.

4.5 Withdrawal Criteria

The subject may be withdrawn from the trial if judged non-compliant with the study procedures or if there is a safety concern, at the discretion of the investigator.

The subject may withdraw from the study at any time.

For subjects withdrawn prematurely, assessments should be completed up to the time of withdrawal.

Patients who require treatment of acute attacks with open label Panhematin™ are not withdrawn from the study.

Patients withdrawn will be offered standard of care treatment, which may include Panhematin™, at the study site or through their own physician.

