This study, as well as the study in acute attacks, will not provide definitive evidence to support the changes in product labeling for Panhematin[™] in the U.S., but will contribute significantly to the body of evidence to support current expert recommendations in the following areas. 1) Current expert opinion is that at least for acute attacks, hemin treatment should be started promptly, without an initial trial of glucose ⁹. Product labeling recommends treatment with Panhematin[™] only after a trial of glucose for several days is not successful. Glucose loading is sometimes effective for treating mild acute attacks ⁹, but is seldom effective for preventing recurrent attacks, and often leads to unwanted weight gain. This study will likely provide evidence to support initial treatment with Panhematin[™] for prevention of frequently occurring attacks. 2) Although Panhematin[™] labeling states that treatment is approved only for treatment of women with attacks of AIP related to the menstrual cycle, there is no evidence from previous cases series

Porphyria Laboratory and Center Date: June 18, 2019 IND 13,929

that treatment response to hemin is different in men, in women when the attack is not related to the cycle or in HCP and VP. Therefore, this study will support the use of hemin for prevention of recurrent attacks of AIP, HCP or VP in men and in women with frequently recurring attacks unrelated to the menstrual cycle. 3) The study will provide evidence to support use of Panhematin[™] reconstituted with 25% human albumin to enhance stability and reduce side effects ⁵⁰ by demonstrating a low incidence of infusion site adverse effects. This method has become widely used in clinical practice, but published data supporting its use is limited. 4) The study will also focus on a dose of 4 mg/kg rather than the 1-4 mg/kg daily recommended in product labeling.

2. Objectives

Patients available for this trial will already be on a prophylactic hemin regimen, and as part of the study will be offered the usual number of periodic prophylactic hemin (or placebo) infusions, which for most patients will be a single weekly infusion. Patients will be offered blinded infusions that correspond to the number of infusions they usually receive within approximately one week for prophylactic treatment.

Primary Objectives:

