3.1 Type of Trial

The trial is a double-blind, randomized, placebo-controlled, parallel group trial investigating the efficacy and safety of Panhematin[™] for preventing acute attacks in at least 20 patients with well-documented acute porphyria (AIP, HCP or VP). These patients will (1.) have had frequent attacks in the past, with symptoms such as abdominal, back and/or limb pain and diagnosed after exclusion of other causes, and (2.) be on hemin prophylaxis for prevention of frequent attacks. Although clear guidelines have not been developed, it is expected that patients will have had 6 or more attacks in one year before starting hemin prophylaxis. This would be considered justification for a preventive regimen of hemin on clinical grounds. Most patients on hemin prophylaxis are given a single dose once weekly. However, other prophylactic regimens are effective in some patients, such as twice weekly infusions or a series of 3-4 infusions at monthly intervals. Giving only one blinded infusion may not be meaningful for a patient for whom more than a single infusion is needed to prevent attacks. Therefore, patients will

be offered the number of blinded infusions they usually are given within approximately one week for prophylaxis. All infusions for each patient will be either Panhematin[™] or placebo. An interim analysis will be carried out after completion of ~10 patients to assess progress and possibly adjust the sample size. The trial consists of the following:

- A screening visit to determine eligibility and obtain informed consent
- A treatment visit for administration of one or more double blind prophylactic doses of Panhematin[™] or placebo, corresponding to each patient's usual prophylactic regimen. Depending on the regimen, this visit may be completed in one day or after the number of days corresponding to their usual prophylactic regimen over approximately one week.
- Follow up visit at 1, 2, 3, and 4 weeks to assess response to the infusion of Panhematin[™] or placebo. These visits will be in person or by telephone.
- Additional visits may be scheduled if needed, for example for treatment of symptoms.
- Follow-up visits 3 and 6 months after the end of treatment either in person or by telephone

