5.5 Blinding

Blinding of treatment with a darkly colored, intravenous drug poses significant challenges, but is feasible because the drug is administered only once, and personnel directly involved in drug reconstitution and administration will be different from those who establish intravenous access and are otherwise involved in the study patient's care. The PI, other physicians, study coordinators and nurses involved in patient care will remain blinded. As described above (Section 5.2), pharmacy personnel (1-2 individuals) and one study nurse who will administer the drug will not be blinded. Blinded staff will not be in the room during study drug administration. Every effort will be made to avoid compromise in blinding if, for example, there are problems with the infusion after it is started. Problems with the infusion will be handled by the unblinded nurse without compromising blinding of other personnel, if possible. Any difficulties that might compromise blinding will be recorded.

Porphyria Laboratory and Center Date: June 18, 2019 IND 13,929

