6.1 Visit Procedures

Visits are designated as shown below to facilitate scheduling of procedures and recording of study-related data. All study visits will be numbered as a single consecutive series. Variations outside specific windows will be recorded as a protocol deviations.

Visit 1	Screening and enrollment. (If screening and enrollment require more than one visit, they will be designated 1a, b, etc.)
Visit 2	Administration of Panhematin [™] or placebo. (This visit might be on the same day as Visit 1.) If additional days are needed at the study site, such as for additional doses of study drug for prevention, or for treatment of an attack of porphyria, these will be designated 2a, b, etc.
Visit 3,4,5,6, 7 & 8	These will occur in person or by phone at weekly intervals for the first month to determine efficacy, and 3 and 6 months after completion of blinded treatment to record long terms effects of the study treatment and subsequent course and clinical treatment of the disease

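### Section 4.5 lets observation of a dosed patient end at withdrawal for reasons other than a treated attack, and does not separate stopping infusions from leaving follow-up

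*Combined protocol and SAP*

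**What the plan says.** Section 4.5 gives the investigator discretion: "The subject may be withdrawn from the trial if judged non-compliant with the study procedures or if there is a safety concern". Patients may also leave of their own accord. For anyone withdrawn early the data rule is one sentence: "For subjects withdrawn prematurely, assessments should be completed up to the time of withdrawal". What follows concerns care and not data: "Patients withdrawn will be offered standard of care treatment". One group is protected. Patients who need open-label Panhematin for an attack "are not withdrawn from the study".

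The scheduled observation is a "Follow up visit at 1, 2, 3, and 4 weeks to assess response to the infusion" (section 3.1), then contacts "3 and 6 months after completion of blinded treatment to record long terms effects of the study treatment" (section 6.1). Section 3.1 allows all of these by telephone.

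On dosing, section 2 states: "Patients will be offered blinded infusions that correspond to the number of infusions they usually receive within approximately one week for prophylactic treatment". It expects a single weekly infusion for most patients. Section 5.5 instead says that "the drug is administered only once".

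Section 3.1 defines a completed patient as one with dosing and at least one week of follow-up, or one withdrawn for an adverse event. Section 4.1 replaces non-completers.

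**The concern.** Stopping study treatment and stopping observation are different decisions, and section 4.5 handles them as one. A patient on several infusions may have good reason to stop after the first. A patient whose blinded dosing is over has no further study exposure to avoid, so withdrawal then removes only the data.

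Two things can be lost. One is attack status for the remaining weekly assessments, on which the first primary objective rests. The other is the course of the adverse event that prompted the withdrawal, which bears on the second. The loss need not be balanced between arms. Section 13.1 lists phlebitis, a transient anticoagulant effect, headache and rare severe reactions for hemin, with further risks for albumin, and no known risk for the saline placebo. Safety withdrawals could therefore fall more often on the active arm.

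**Working it through.** **Does anything else in the protocol supply follow-up after withdrawal?**

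- Section 6.3.6 ties adverse event recording to visits, so recording ends when visits end.
- Section 6.3.1 limits new non-porphyria symptoms to the treatment period.
- Section 9 has a medical team member evaluate the patient and write a CRF note when an event occurs. It does not ask for follow-up to resolution.
- Section 11 keeps every exposed patient in the safety analysis, which uses whatever was recorded before withdrawal.
- Section 12.3 lists post-randomization exclusions and assesses their impact, but gives no method for a missing attack outcome.
- Section 14 provides for follow-up only if the trial itself is terminated or suspended.

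None of these closes the gap, and two other provisions pull against the rule in 4.5. Section 3.2 wants efficacy data for 4 weeks or until the next Panhematin treatment, whichever is longer. Section 9 requires the duration of adverse events to be verifiable, which is impossible for an event still open when recording stops.

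**Who is affected?** A patient withdrawn for an adverse event counts as completed under 3.1, so the replacement rule in 4.1 does not reach that patient. Such a patient can be one of the 20 without a week-1 outcome, the result that sections 3.1 and 12.1 emphasize.

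**The plan's own figure.** Section 12.4 gives 80% power with 10 per group at attack probabilities 0.8 and 0.2. The pooled normal approximation (two-sided 5%, no continuity correction) is

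power = Φ[(d − 1.96·√(2·p̄(1−p̄)/n)) / √((p₁(1−p₁)+p₂(1−p₂))/n)].

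With d = 0.6, p̄ = 0.5 and n = 10 this is Φ[(0.6 − 1.96 × 0.2236)/0.1789] = Φ(0.904) = 81.7%. The stated figure is reproduced by this method and is not in dispute here.

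**Effect of missing outcomes.** No withdrawal rate is given, so the counts below are assumptions.

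1. *Proportion.* One unknown outcome among 10 is 1/10, so it can move that arm's attack proportion by up to 10 percentage points.
2. *Test result.* Take the expected table, 8/10 attacks on placebo and 2/10 on Panhematin. Fisher's exact test is used for illustration; the planned analysis is logistic regression.
   - One Panhematin patient is withdrawn without an attack and counted attack-free (8/10 v 2/10). p = 2 × (2025 + 100 + 1)/184,756 = 0.023.
   - The same patient is dropped (8/10 v 2/9). p = (1620 + 90 + 1 + 10 + 405)/92,378 = 0.023.
   - The same patient is followed and found to have had an attack (8/10 v 3/10). p = 2 × (5400 + 450 + 10)/167,960 = 0.070.
   - With two or three such unseen attacks, p = 0.170 or 0.350.

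   With one such patient, neither counting nor dropping the patient would reveal the problem; only the observed outcome does.
3. *Power.* If outcomes are lost without replacement, the formula above gives 76.8% with 9 per arm (Φ[(0.6 − 1.96 × 0.2357)/0.1886]) and 70.9% with 8 per arm (Φ[(0.6 − 1.96 × 0.25)/0.2]).

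**The case against.** The best reply is that the gap is narrow and the text permissive. Withdrawal is discretionary. Asking for assessments up to withdrawal sets a minimum and does not forbid later contact. Section 3.1 allows additional visits, and withdrawn patients may be treated at the study site. Investigators are blinded, so they would not be withdrawing by arm. The consent form is not among the material reviewed and may describe contact after withdrawal. All of this stands, and it limits how often data would be lost. It does not turn an optional contact into a required one.

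Four stronger readings are tempting, and the documents do not support them.

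- A reader might infer that the rule drops the very patients who do badly after dosing. The main expected problem is an attack, and attacks treated with open-label Panhematin are expressly not a reason for withdrawal.
- A reader might treat this as a one-infusion trial in which withdrawal can never reduce exposure. Sections 2 and 3.1 allow several infusions within about a week, so for some patients it can.
- A reader might count nearly all of the 4 weeks as lost primary follow-up. The plan puts its emphasis on week 1, and later weeks say less about a short-acting drug.
- A reader might apply the 10-point shift to adverse events. A patient withdrawn because of an event already counts as having one, so what is lost is its duration and outcome.

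For a non-compliant patient, section 11 may exclude the case from the efficacy analysis anyway, so extra contacts may recover less there. Section 12 also specifies no analysis of the month 3 and 6 contacts, so their value is mainly for safety.

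**Conclusion.** The point holds in a limited form. For a dosed patient withdrawn for a safety concern other than a treated attack, for non-compliance or by choice, the protocol requires no observation after withdrawal, and no other section restores it. The definition of a completed patient lets an adverse event withdrawal count toward the 20 without a week-1 attack outcome.

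The size cannot be estimated, because no withdrawal rate is given. The illustration assumes 10 per arm, the plan's 0.8 versus 0.2 scenario, exactly the expected counts, and one withdrawn Panhematin patient with an unseen attack. On those assumptions a result at p = 0.023 would have been 0.070, so one patient can change the conclusion. With no such withdrawals there is no effect. This is a cheap improvement and not a flaw that invalidates the design.

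**What to change.** Replace the data sentence in section 4.5 with wording that does three things:

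- Distinguish stopping blinded infusions from withdrawing consent to follow-up.
- Keep every patient who has received any blinded infusion in the week 1-4 and month 3 and 6 contacts, by telephone where needed, for attack status and adverse events.
- Continue to record adverse events open at that time until they are resolved or stable.

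Only the patient's withdrawal of consent to contact would end data collection. When to stop infusions stays with the investigator as now written. With this change, the completed-patient definition in 3.1 no longer gives up a week-1 outcome that could have been obtained. The single-dose wording in sections 3.1 and 5.5 should be reconciled with the multiple-infusion wording in sections 2 and 3.1, so that it is clear when a patient's dosing is over.

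The cost is a protocol amendment and minor coordinator time for contacts that are already scheduled. The sample size and the stated power do not change.
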